19 CONDITIONS FOR MODIFYING THE PROTOCOL

Protocol modifications to ongoing studies must be made only after consultation between a Kadmon representative and the investigator. Protocol modifications will be prepared, reviewed, and approved by Kadmon representatives.

All protocol modifications must be submitted to the IRB for information and approval in accordance with local requirements, and to regulatory agencies if required. Approval must be obtained before any changes can be implemented, except for changes necessary to eliminate an immediate hazard to study subjects, or when the change involves only logistical or administrative aspects of the trial (e.g. change in monitor, change of telephone number) or to eliminate an immediate hazard to study subjects. In these circumstances, immediate approval of the chairman of the IRB must be sought, and the investigator should inform Kadmon, and the full IRB within 5 business days after the emergency occurs.

20 CONDITIONS FOR TERMINATING THE STUDY

Kadmon has the right to terminate the study at any time. In terminating the study, Kadmon and the investigator will ensure that adequate consideration is given to the protection of the subjects' interests.

The following data and materials are required by Kadmon before a study can be considered to be complete or terminated:

- Laboratory findings, clinical data, and all special test results from screening through the end of the study, including the follow-up period for all enrolled subjects;
- Case Report Forms/Records. Electronic case report forms (eCRFs) will be used in this study. Records (including correction forms) for all enrolled subjects will be properly completed by appropriate study personnel, and signed and dated by the principal investigator, as required;
- Principal investigator sign-off of all required eCRF forms;
- Completed Drug Accountability Records, Drug Inventory Log, and Inventory of Returned Drug forms or documentation of destruction, as appropriate;
- Return of all unused study drug to Kadmon unless an alternate disposition method is agreed upon at study initiation by Kadmon and investigational site(s);
- Copies of protocol amendments and other documents, and IRB approval/notification, as applicable;
- A summary of the study prepared by the principal investigator (IRB summary closure letter is an acceptable equivalent).

21 STUDY DOCUMENTATION, CRFS, AND RECORD KEEPING

21.1 Investigator's Files and Retention of Documents

The investigator must maintain adequate and accurate records to enable the conduct of the study to be fully documented and the study data to be subsequently verified. These documents should be classified into two separate categories as follows: (1) investigator's study file and (2) subject clinical source documents.

The investigator's study file will contain the protocol and protocol amendments, eCRFs, query forms, IRB and governmental approval with correspondence, sample informed consent, drug records, staff curriculum vitae and authorization forms, and other appropriate documents and correspondence.

Subject clinical source documents (usually predefined by the project to record key efficacy and safety parameters independent of the eCRFs) may include subject hospital/clinic records, physician's and nurse's notes, appointment book, original laboratory reports, ECG, X-ray, pathology and special assessment reports, signed ICFs, consultant letters, email communication and subject screening and enrollment logs. The investigator must keep these two categories of documents on file for at least 2 years following the marketing application approval date for the study treatment and for the indication being investigated or for 2 years after the investigation is discontinued and the FDA is notified. After that period of time, the documents may be destroyed subject to local regulations with prior written permission from Kadmon. If the investigator wants to assign the study records to another party or move them to another location, Kadmon must be notified in advance.

If the investigator cannot guarantee the archiving requirement at the study site for any or all of the documents, special arrangements must be made between the investigator and Kadmon to store these in a sealed container outside of the study site so that they can be returned sealed to the investigator in case of a regulatory audit. When source documents are required for the continued care of the subject, appropriate copies should be made for storing outside of the study site.

21.2 Source Documents and Background Data

Investigators must maintain adequate and accurate source documents on which the eCRFs for each subject are based. They are separate and distinct from the eCRFs.

These records include detailed notes on:

- Medical history;
- Date and time of informed consent with HIPAA authorization either contained in the ICF or presented to the subject candidate as a standalone document;
- Description of the complete consenting process;
- The basic identifying information that linked the subject's medical record with the eCRFs;
- The results of all diagnostic tests performed, diagnoses made, therapy provided, and any other data on the condition of the subject;
- The medical condition of the subject during their involvement in the study;
- All AEs;
- The subject's exposure to the study medication;
- The subject's exposure to any concomitant therapy;
- All relevant observations and data on the condition of the subject throughout the trial;
- Justification for all entries in the subject's eCRF;
- Radiology images (hard copy and digital), and reports if required;
- Death information and any available autopsy data.

A subject log of all potentially eligible subjects considered, but not consented, for obvious deviations from the entry criteria, will be kept at each site. The log will contain subjects' initials, diagnosis, eligibility, or, if not eligible, reason for not consenting. All consented subjects will be logged, regardless of whether they ultimately enroll.

Upon request, the investigator will supply Kadmon with any required background data from the study documentation or clinic records. In case of special problems or governmental queries or requests for audit inspections, it is also necessary to have access to the complete study records, provided that subject confidentiality is protected.

21.3 Audits and Inspections

The investigator should understand that source documents for this study should be made available to appropriately qualified personnel from the Kadmon Quality Assurance Unit (or

designee), or to health authority inspectors after appropriate notification. The verification of the eCRF data must be by direct inspection of source documents.

21.4 Electronic Case Report Forms

Clinical trial data for this study will be captured on electronic case report forms (eCRF) designed for computer processing and analysis. This computerized system will be validated and compliant with 21 CFR Part 11. Corrections to data will be made according to 21 CFR Part 11, Electronic Records; Electronic Signatures. There will also be an electronic audit trail. The investigator agrees to provide all information requested on the eCRF in an accurate manner according to instructions provided. The investigator should ensure the accuracy, completeness, and timeliness of the data reported to Kadmon in the eCRF and in all required reports.

An eCRF is required to be submitted for every subject who receives any amount of study drug. This includes submission of retrievable data on subjects who withdraw before completion of the study. Prior to submission, eCRFs must be reviewed for completeness and accuracy, and signed and dated where indicated by the principal investigator or authorized delegate from the study staff. If a subject stops treatment or terminates from the study, the dates and reasons must be noted on the eCRF.

22 MONITORING THE STUDY

All aspects of the study will be carefully monitored by Kadmon or authorized representatives according to GCP and standard operating procedures (SOPs) for compliance with applicable government regulations.

It is understood that the responsible Kadmon study monitor (or designee) will contact and visit the investigator regularly and will be allowed on request to inspect the various records of the trial (eCRFs and other pertinent data) provided that subject confidentiality is maintained in accordance with local requirements. The principal investigator and key trial personnel must be available to assist the monitor during these visits. The investigator (or designee) must agree to cooperate with the monitor to ensure that any problems detected during the course of these monitoring visits are resolved.

It will be the monitor's responsibility to inspect the eCRFs in comparison to source documents at regular intervals throughout the study according to the monitoring plan, to verify the adherence to the protocol and the completeness, consistency, and accuracy of the data being entered on them and clarifying any data queries. The monitor should have access to laboratory test reports and other subject records needed to verify the entries on the eCRF. The completed and corrected eCRFs/CRFs for completed visits will either be collected by the monitor at the end of the study or obtained electronically for data processing. The investigator is responsible for the timely completion of eCRFs by assigned study staff. The eCRFs must be completed within seven (7) days of the subject's visit. A copy of the eCRFs will be retained by the investigator who must ensure that it is stored in a secure place with other study documents, such as the protocol, the Investigator's Brochure, and any protocol amendments.

Upon completion of the study, the monitor will make a final assessment of the conduct of the study and inventory all clinical supplies to be returned to Kadmon.

23 CONFIDENTIALITY OF TRIAL DOCUMENTS AND SUBJECT RECORDS

The investigator must ensure that subjects' anonymity will be maintained and that their identities are protected from unauthorized parties. On eCRFs or other documents submitted to Kadmon and the IRB, subjects should be identified by an identification code and/or initials and not by their names. The investigator should keep a subject enrollment log showing codes, names, and addresses. The investigator should maintain documents not for submission to Kadmon (e.g. subjects' written consent forms) in strict confidence.

Authorized regulatory officials and Kadmon personnel (or their representatives) will be allowed full access to inspect and copy the records. All study drug, subject bodily fluids and tissue, and/or other materials collected shall be used solely in accordance with this protocol, unless otherwise agreed to in writing by Kadmon.

The principal investigator also agrees that all information received from Kadmon, including but not limited to the Investigator's Brochure, this protocol, eCRFs, the investigational new drug, and any other study information remain the sole and exclusive property of Kadmon during the conduct of the study and thereafter. This information is not to be disclosed to any third party (except employees or agents directly involved in the conduct of the study or as required by law) without prior written consent from the Sponsor. The principal investigator further agrees to take all reasonable precautions to prevent the disclosure by any employee or agent of the study site to any third party or otherwise into the public domain.

24 PUBLICATION OF DATA AND PROTECTION OF TRADE SECRETS

The results of this study may be published or presented at scientific meetings. The investigator agrees to submit all manuscripts or abstracts to Kadmon for review at least 30 days before submission. This allows Kadmon to protect proprietary information and to provide comments based on information from other studies that may not yet be available to the investigator.

In the event that Kadmon coordinates a publication or presentation of study results from all study sites, the participation of investigator or other representatives of study site as a named author shall be determined in accordance with Kadmon policy and generally accepted standards for authorship.

Evaluable for objective response: Only those subjects who have measurable disease present at screening, have received at least 2 cycles of therapy, and have had their disease re-evaluated will be considered evaluable for response. These subjects will have their response classified according to the definitions stated below. (Note: Subjects who exhibit objective disease progression prior to the end of Cycle 2 will also be considered evaluable.)

Evaluable Non-Target Disease Response: Subjects who have lesions present at screening that are evaluable but do not meet the definitions of measurable disease, have received at least 2 cycles of therapy, and have had their disease re-evaluated will be considered evaluable for non-target disease. The response assessment is based on the presence, absence, or unequivocal progression of the lesions.

Disease Parameters

Measurable disease: Measurable lesions are defined as those that can be accurately measured in at least 1 dimension (longest diameter for non-nodal lesions and short axis for nodal lesions to be recorded) as ≥ 20 mm by chest X-ray, as ≥ 10 mm with chest, abdominal, or pelvic CT scan or with MRI of brain, or ≥ 10 mm with calipers by clinical exam. All tumor measurements must be recorded in millimeters (or decimal fractions of centimeters).

Note: Tumor lesions that are situated in a previously irradiated area may be considered measurable if they have increased in size.

Malignant lymph nodes: To be considered pathologically enlarged and measurable, a lymph node must be ≥ 15 mm in short axis when assessed by CT scan (CT scan slice thickness recommended to be no greater than 5 mm). At Screening and in follow-up, only the short axis will be measured and followed.

Non-measurable disease: All other lesions (or sites of disease), including small lesions (longest diameter <10 mm or pathological lymph nodes with ≥ 10 to <15 mm short axis), are considered non-measurable disease. Bone lesions, leptomeningeal disease, ascites, pleural/pericardial effusions, lymphangitis cutis/pulmonitis, inflammatory breast disease, and abdominal masses (not followed by CT or MRI), are considered as non-measurable.

Note: Cystic lesions that meet the criteria for radiographically defined simple cysts should not be considered as malignant lesions (neither measurable nor non-measurable) since they are, by definition, simple cysts.

‘Cystic lesions’ thought to represent cystic metastases can be considered as measurable lesions, if they meet the definition of measurability described above. However, if non-cystic lesions are present in the same subject, these are preferred for selection as target lesions.

Target lesions: All measurable lesions up to a maximum of 2 lesions per organ and 5 lesions in total, representative of all involved organs, should be identified as **target lesions** and recorded and measured at Screening. Target lesions should be selected on the basis of their size (lesions with the longest diameter), be representative of all involved organs, but in addition should be those that lend themselves to reproducible repeated measurements. It may be the case that, on occasion, the largest lesion does not lend itself to reproducible measurement in which circumstance the next largest lesion which can be measured reproducibly should be selected. A sum of the diameters (longest for non-nodal lesions, short axis for nodal lesions) for all target lesions will be calculated and reported as the Screening sum diameters. If lymph nodes are to be included in the sum, then only the short axis is added into the sum. The Screening sum diameters will be used as reference to further characterize any objective tumor regression in the measurable dimension of the disease.

Non-target lesions: All other lesions (or sites of disease) including any measurable lesions over and above the 5 target lesions should be identified as **non-target lesions** and should also be recorded at Screening. Measurements of these lesions are not required, but the presence, absence, or in rare cases unequivocal progression of each should be noted throughout follow-up.

Methods for Evaluation of Measurable Disease

All measurements should be taken and recorded in metric notation using a ruler or calipers. All Screening evaluations should be performed as closely as possible to the beginning of treatment and never more than 4 weeks before the beginning of the treatment.

The same method of assessment and the same technique should be used to characterize each identified and reported lesion at Screening and during follow-up. Imaging-based evaluation is preferred to evaluation by clinical examination unless the lesion(s) being followed cannot be imaged but are assessable by clinical exam.

Clinical lesions: Clinical lesions will only be considered measurable when they are superficial (e.g. skin nodules and palpable lymph nodes) and ≥ 10 mm diameter as assessed using calipers (e.g. skin nodules). In the case of skin lesions, documentation by color photography, including a ruler to estimate the size of the lesion, is recommended.

Chest X-ray: Lesions on chest X-ray are not acceptable as measurable lesions in this study.

Conventional CT and MRI: This guideline has defined measurability of lesions on CT scan based on the assumption that CT slice thickness is 5 mm or less. If CT scans have slice thickness greater than 5 mm, the minimum size for a measurable lesion should be twice the slice thickness. MRI in this study is required for evaluation for brain metastases.

FDG-PET-CT: Not acceptable for this study.

Ultrasound: Not acceptable for this study.

Endoscopy, Laparoscopy: Not acceptable for this study.

FDG-PET: Not acceptable for this study.

Response Criteria

Evaluation of Target Lesions

- Complete Response (CR):** Disappearance of all target lesions. Any pathological lymph nodes (whether target or non-target) must have reduction in short axis to < 10 mm.
- Partial Response (PR):** At least a 30% decrease in the sum of the diameters of target lesions, taking as reference the Screening sum diameters.
- Progressive Disease (PD):** At least a 20% increase in the sum of the diameters of target lesions, taking as reference the smallest sum on study (this includes the Screening sum if that is the smallest on study). In addition to the relative increase of 20%, the sum must also demonstrate an absolute increase of at least 5 mm. (Note: the appearance of 1 or more new lesions is also considered progression).
- Stable Disease (SD):** Neither sufficient shrinkage to qualify for PR nor sufficient increase to qualify for PD, taking as reference the smallest sum

diameters while on study.

Note for subjects with scans that are on the “borderline” of disease progression (e.g. 21% increase in sum of target lesion diameters) but for whom the investigator determines a clinical benefit: These subjects will be allowed to continue in the study after discussion with the medical monitor. If improvement is documented at the next subsequent staging time point (e.g. 17% increase), the subject will continue on study. If worsening is documented (e.g. 30% increase in sum of target lesion diameters), the subject should be discontinued from the study, and the progression date should be the original date on which “borderline” disease progression was first documented.

Target lesions that become “too small to measure”.

While on study, all lesions (nodal and non-nodal) recorded at Cycle 1 Day 1 should have their actual measurements recorded at each subsequent evaluation, even when very small (e.g. 2 mm). However, sometimes lesions or lymph nodes which are recorded as target lesions at Cycle 1 Day 1 become so faint on CT scan that the radiologist may not feel comfortable assigning an exact measure and may report them as being “too small to measure”. When this occurs it is important that a value be recorded on the case report form. If it is the opinion of the radiologist that the lesion has likely disappeared, the measurement should be recorded as 0mm. If the lesion is believed to be present and is faintly seen but too small to measure, a default value of 5mm should be assigned. (Note: It is less likely that this rule will be used for lymph nodes since they usually have a definable size when normal and are frequently surrounded by fat such as in the retroperitoneum; however, if a lymph node is believed to be present and is faintly seen but too small to measure, a default value of 5 mm should be assigned in this circumstance as well). This default value is derived from the 5 mm CT slice thickness (but should not be changed with varying CT slice thickness). The measurement of these lesions is potentially non-reproducible; therefore providing this default value will prevent false responses or progressions based upon measurement error. To reiterate, however, if the radiologist is able to provide an actual measure, that should be recorded, even if it is below 5 mm.

Evaluation of Non-Target Lesions

Complete Response (CR): Disappearance of all non-target lesions and normalization of tumor marker level. All lymph nodes must be non-pathological in size (< 10 mm short axis).

Note: If tumor markers are initially above the upper normal limit, they must normalize for a subject to be considered in complete clinical response.

Non-CR/Non-PD: Persistence of 1 or more non-target lesion(s) and/or

maintenance of tumor marker level above the normal limits.

Progressive Disease (PD): Appearance of 1 or more new lesions and/or *unequivocal progression* of existing non-target lesions. *Unequivocal progression* should not normally trump target lesion status. It must be representative of overall disease status change, not a single lesion increase.

Although a clear progression of “non-target” lesions only is exceptional, the opinion of the treating physician should prevail in such circumstances, and the progression status should be confirmed at a later time by the review panel (or principal investigator).

Evaluation of Best Overall Response

The best overall response is the best response recorded from the start of the treatment until disease progression/recurrence (taking as reference for progressive disease the smallest measurements recorded since the treatment started). The subject's best response assignment will depend on the achievement of both measurement and confirmation criteria.

For Subjects with Measurable Disease (i.e., Target Disease)

Target Lesions	Non-Target Lesions	New Lesions	Overall Response	Best Overall Response when Confirmation is Required*
CR	CR	No	CR	≥ 4 wks. Confirmation**
CR	Non-CR/Non-PD	No	PR	
CR	Not evaluated	No	PR	
PR	Non-CR/Non-PD/not evaluated	No	PR	≥ 4 wks. Confirmation**
SD	Non-CR/Non-PD/not evaluated	No	SD	Documented at least once ≥ 4 wks. from Screening**
PD	Any	Yes or No	PD	No prior SD, PR or CR
Any	PD***	Yes or No	PD	
Any	Any	Yes	PD	

* See RECIST 1.1 manuscript for further details on what is evidence of a new lesion.

** Only for non-randomized trials with response as primary endpoint.

*** In exceptional circumstances, unequivocal progression in non-target lesions may be accepted as disease progression.

Note: Subjects with a global deterioration of health status requiring discontinuation of treatment without objective evidence of disease progression at that time should be reported as “*symptomatic deterioration.*” Every effort should be made to document the objective progression even after discontinuation of treatment.

For Subjects with Non-Measurable Disease (i.e., Non-Target Disease)

Non-Target Lesions	New Lesions	Overall Response
CR	No	CR
Non-CR/non-PD	No	Non-CR/non-PD*
Not all evaluated	No	Not evaluated
Unequivocal PD	Yes or No	PD
Any	Yes	PD

* 'Non-CR/non-PD' is preferred over 'stable disease' for non-target disease since SD is increasingly used as an endpoint for assessment of efficacy in some trials so to assign this category when no lesions can be measured is not advised

Note for subjects with scans that are on the “borderline” of disease progression (e.g. 21% increase in sum of target lesion diameters) but for whom the investigator determines a clinical benefit: These subjects will be allowed to continue in the study after discussion with the medical monitor. If improvement is documented at the next subsequent staging time point (e.g. 17% increase), the subject will continue on study. If worsening is documented (e.g. 30% increase in sum of target lesion diameters), the subject should be discontinued from the study, and the progression date should be the original date on which “borderline” disease progression was first documented.

Duration of Response

Duration of overall response: The duration of overall response is measured from the time measurement criteria are met for CR or PR (whichever is first recorded) until the first date that recurrent or progressive disease is objectively documented (taking as reference for progressive disease the smallest measurements recorded since the treatment started).

The duration of overall CR is measured from the time measurement criteria are first met for CR until the first date that progressive disease is objectively documented.

Duration of stable disease: Stable disease is measured from the start of the treatment until the criteria for progression are met, taking as reference the smallest measurements recorded since the treatment started, including the Screening measurements.

Progression-Free Survival

PFS will be calculated as a secondary endpoint for all subjects and will represent the time between initiation of therapy to the time of documentation of progression of disease or death.

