16 STATISTICAL CONSIDERATIONS

All descriptive and inferential statistical analyses will be performed using the most recently released and available SAS statistical software, unless otherwise noted. For categorical variables, the number and percent of each category within a parameter will be calculated for non-missing data. For continuous variables, the mean, median, and standard deviation, as well as the minimum and maximum values, will be presented. The summary of time-to-event variables will include Kaplan-Meier methods as appropriate.

Statistical significance will be declared when the two-tailed p-value is found to be less than or equal to 0.05, unless otherwise noted. Missing data will not be imputed unless otherwise stated. All clinical data captured will be provided in data listings.

Additional statistical details will be provided in a prospective statistical plan.

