16.2 Sample Size Justification

For Cohort A, assuming that 20% of subjects with BM have RECIST 1.1 response (CR or PR), the study has an approximately 80% chance of having at least 3 subjects with RECIST 1.1 response, and an over 90% chance of at least 2 subjects having a response. All subjects who take at least one dose of study drug will be evaluable for safety and efficacy assessments.

For Cohort B, assuming that 20% of subjects with LM have improvement in at least one symptom or sign attributed to leptomeningeal metastases, the study has an approximately 80% chance of having at least 3 subjects with improvement in at least one symptom or sign attributed to leptomeningeal metastases and an over 90% chance of at least 2 subjects having improvement attributed to leptomeningeal metastases. All subjects who take at least one dose of study drug will be evaluable for safety and efficacy assessments.

For Cohort C, assuming that 20% of subjects with BM have RECIST 1.1 response (CR or PR), the study has an approximately 80% chance of having at least 3 subjects with RECIST 1.1 response, and an over 90% chance of at least 2 subjects having a response. All subjects who take at least one dose of study drug will be evaluable for safety and efficacy assessments.

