16.3 Statistical Considerations

16.3.1 Study Populations

Adult subjects with NSCLC who have progressed with BM or LM, or who have brain metastases at initial presentation, will be enrolled.

All subjects who take at least one dose of study drug will be evaluable for safety and efficacy assessments.

Subjects who do not complete the study, for whatever reason, will have all available data (up until the time of termination related to the reason they were terminated) included in the analysis. Completion of the study will be defined as completion of the first cycle of study drug administration, or discontinuation prior to that time for an AE.

The PK population will consist of all subjects who receive at least one dose of tesevatinib, and who have at least one sample for PK for a dosing interval.

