16.3.6 Efficacy/Activity

Descriptive statistics, including 95% confidence intervals for improvement in symptoms attributed to leptomeningeal metastases, clearing of NSCLC cells in the CSF, and clearing of CNS MRI findings will be presented. Exploratory evaluation of efficacy results by EGFR mutation will be performed.

Efficacy/Activity analyses will present results by Cohort and, where appropriate, the three cohorts combined.

In addition, identical statistics for the change and percent change from Cycle 1 Day 1 tumor measurements will be presented. These analyses will be done after each two cycles of therapy, and will include peripheral (non-CNS) tumors as well as brain metastases. Summary statistics will be produced for PFS and OS. The percentage of subjects without disease progression after 3 and 6 months of dosing will also be presented separately by local and central radiograph results.

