## 1.2.1 Sample Size Justification

For Cohort A, assuming that 20% of subjects with BM have response (complete response [CR] or partial response [PR]), N=20 has an approximately 80% chance of

having at least 3 subjects with response, and an over 90% chance of at least 2 subjects having a response.

For Cohort B, assuming that 20% of subjects with LM have improvement in at least one symptom or sign attributed to LM, N=20 has an approximately 80% chance of having at least 3 subjects with improvement in at least one symptom or sign attributed to leptomeningeal metastases and an over 90% chance of at least 2 subjects having improvement attributed to LM.

For Cohort C, assuming that 20% of subjects with BM have response (CR or PR), N=20 has an approximately 80% chance of having at least 3 subjects with response, and an over 90% chance of at least 2 subjects having a response.

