### 1.2.5 Analysis Populations

All subjects who take at least one dose of study drug will be included in efficacy and safety analysis. Non-evaluable response will be classified as non-responder.

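### The protocol's efficacy denominators conflict: the SAP settles the response rate, but the 3- and 6-month non-progression percentages have no estimator and no rule for deaths or early exits

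*Protocol*

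**What the plan says.** **Response.** Protocol Appendix A restricts evaluability for objective response: "Only those subjects who have measurable disease present at screening, have received at least 2 cycles of therapy" and have been re-evaluated. A note adds back subjects with objective progression before the end of Cycle 2. Protocol 16.3.1 says otherwise: "All subjects who take at least one dose of study drug will be evaluable for safety and efficacy assessments". Protocol 16.2 repeats that sentence for each cohort. SAP 1.2.5 also includes everyone with at least one dose and adds "Non-evaluable response will be classified as non-responder". SAP Table 1 puts both response-rate tables on all treated subjects, with exact confidence intervals.

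**General rule.** Protocol Section 16 states that for categorical variables "the number and percent of each category within a parameter will be calculated for non-missing data", and that missing data are not imputed unless otherwise stated. It provides Kaplan-Meier methods for time-to-event variables, as appropriate.

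**3- and 6-month rates.** Protocol 16.3.6 plans "The percentage of subjects without disease progression after 3 and 6 months of dosing", separately by local and central reading. The objectives and SAP 1.3.1.2 name a CNS non-progression rate at 3 and 6 months as a secondary endpoint. SAP Table 1 has tables and Kaplan-Meier figures for PFS, OS and both times to progression, but no row for this rate.

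**The concern.** A subject who stops for toxicity, withdraws or dies before the end of Cycle 2 without documented objective progression is not evaluable under Appendix A, but is evaluable under 16.2 and 16.3.1. The protocol therefore contradicts itself. The SAP decides the matter for response. It does not define non-evaluable, so a reader who looks for a definition is sent back to Appendix A.

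The 3- and 6-month percentages have no such rule. The SAP's non-responder sentence covers response only, so the stated default is a percentage of non-missing data. Missing status is likely in this trial. Tables 4-1 and 4-2 schedule no tumor assessment after the end-of-treatment visit, and long-term contact is by telephone for survival and further therapy, although the synopsis says that follow-up for progression continues. A subject who dies or leaves early without documented progression would have no status at 3 or 6 months and would drop out of the percentage. These are single-arm cohorts of at most 20, reported descriptively, and discontinued subjects are not replaced, so each subject dropped moves the figure visibly.

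**Working it through.** **1. Which denominator the sample-size statement fits.** Inputs: up to 20 per cohort and an assumed 20% response rate (Protocol 16.2; SAP 1.2.1). The claim is "the study has an approximately 80% chance of having at least 3 subjects with RECIST 1.1 response", and over 90% for at least 2.

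P(X ≥ 3) = 1 − [0.8^20 + 20 × 0.2 × 0.8^19 + 190 × 0.2² × 0.8^18] = 1 − [0.0115 + 0.0576 + 0.1369] = 0.794.

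P(X ≥ 2) = 1 − [0.0115 + 0.0576] = 0.931.

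Both figures reproduce with n = 20. The table shows what happens if early exits without progression are removed. The documents give no exit count, so 2, 4 and 6 are assumptions, as are the 4 responders. Intervals are Clopper-Pearson 95%.

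| Removed | n | P(≥ 3 responders) | P(≥ 2 responders) | Rate with 4 responders |
|---|---|---|---|---|
| 0 | 20 | 79.4% | 93.1% | 20.0% (5.7-43.7) |
| 2 | 18 | 72.9% | 90.1% | 22.2% (6.4-47.6) |
| 4 | 16 | 64.8% | 85.9% | 25.0% (7.3-52.4) |
| 6 | 14 | 55.2% | 80.2% | 28.6% (8.4-58.1) |

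The 80% statement matches only the all-treated row.

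**2. Reach of Appendix A.** Its heading limits it to non-CNS response. However, its measurability definition includes brain MRI. Protocol 11.1.1 sends the reader to Appendices A and B for both CNS and non-CNS progression, and Appendix B is the ECOG scale. No other RECIST text is given for brain metastases, so Appendix A is the only one available for the primary endpoint of Cohorts A and C. It does not define Cohort B's primary endpoint, which is CTCAE symptom improvement.

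**3. 3- and 6-month percentage, crude.** Assume 20 treated, 8 known to be progression-free at the landmark, and 2, 4 or 6 of missing status.

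- All treated, missing counted as failure: 8/20 = 40.0% (19.1-63.9).
- Missing dropped: 8/18 = 44.4% (21.5-69.2), 8/16 = 50.0% (24.7-75.3), 8/14 = 57.1% (28.9-82.3).

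The 40% is the floor. It is the correct figure for PFS if the missing subjects are deaths, because Appendix A counts death as a PFS event.

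**4. The same cohort by Kaplan-Meier, 6 missing.** Then 20 − 8 − 6 = 6 have progressed.

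- All 6 missing are deaths (PFS): 8/20 = 40.0%.
- All 6 are censored before the first progression: 8/14 = 57.1%.
- All 6 are censored after the last progression but before the landmark: 14/20 = 70.0%.

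The result depends on why and when subjects leave. The non-missing percentage ignores both.

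**The case against.** The strongest reply is that the texts can be read together. Appendix A says who is evaluable and states no analysis denominator; the SAP says that the non-evaluable count as non-responders; Section 16 yields where something else is stated, and SAP 1.2.5 states it. Protocol 16.3.1 also keeps all available data from subjects who do not complete. For the response rate this stands. A reader might infer that early toxicity dropouts and deaths leave the primary response rate. The planned tables do not support that; it would happen only if Appendix A were applied in place of the SAP.

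For the 3- and 6-month rates, the reply is that Kaplan-Meier is provided for time-to-event variables, with deaths as PFS events and exits censored, so nobody is discarded outright. That is a sound method, but neither document assigns it to these rates, and 16.3.6 describes a percentage.

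A reader might also infer that the months-of-dosing wording makes the figure near 100% by construction. The text does not restrict the denominator to subjects still on drug, the SAP endpoint has no dosing qualifier, and subjects with oligoprogressive disease may continue treatment while counted as progressed. That is one extreme reading of loose wording.

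Finally, the SAP plans no formal testing and no decision threshold is stated, which limits the consequences.

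**Conclusion.** The point holds in two parts of unequal weight.

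For the response rate there is a wording conflict inside the protocol that the SAP resolves. The planned analysis is all treated, and the sample-size figure agrees with it. If the narrower rule were used, removing 2 to 6 subjects would move 20.0% to 22.2-28.6%.

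For the 3- and 6-month rates the gap is real. The stated default drops deaths and early exits without documented progression, and no rule overrides it. In the assumed example the figure rises from 40% to 44-57%. The upward direction is certain for deaths when the endpoint is PFS, and likely for exits due to clinical deterioration. For exits unrelated to prognosis, the direction depends on timing, as step 4 shows. The counts of responders, exits and progression-free subjects are all assumptions; the documents give none.

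**What to change.** 1. Add a sentence to Appendix A: its evaluability definition does not set the denominator of the response rate, which is all treated subjects with non-evaluable counted as non-response, as in SAP 1.2.5. Keep the definition, because the SAP rule needs it, and say whether the appendix applies to brain metastases.
2. Exempt response and the 3- and 6-month rates from the non-missing rule in Protocol Section 16.
3. In 16.3.6 and SAP Section 2, count time from first dose instead of months of dosing. Estimate the 3- and 6-month rates in all treated subjects by Kaplan-Meier with confidence intervals. Death is an event for PFS. For the CNS rate, state how deaths without CNS progression are handled (censored or competing event). Scoring every death or missed scan as failure would turn the CNS rate into a survival composite, so it should not be the default. Because very early censoring has much the same effect as dropping a subject, report the number censored before each landmark, with reasons.
4. Add a table for the CNS non-progression rate to SAP Table 1.

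The cost is wording, one more table and a little more analysis. The landmark rates may look slightly less favorable; the planned response rate does not change.
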